Statistical analysis plan

Title:

Does deciding not to participate in a lifestyle intervention affect the long-term change in psychosocial well-being for children with obesity?

Suggested authors:

[name]

[name]

[name]

[name]

[name]

[name]

Purpose:

In this plan for statistical analysis, we provide an overview of the study's context and objectives, as well as general aspects of data management and data analysis. The statistical analysis plan will be attached as a supplementary document upon submission.

Introduction

Childhood obesity is associated with an increased risk of developing non-communicable lifestyle diseases later in life(1-4), while reduced psychological well-being often occurs during childhood. Children living with obesity suffer from lower self-esteem, which have been associated with increased level of sadness and loneliness(5). They also experience higher degree of bullying/teasing(6, 7), have lower quality of life (8, 9) and increasing risk of depression (10) as compared to their peers living without obesity.

Family-centered lifestyle interventions including a multifactorial approach are still considered the first line of treatment when handling childhood obesity(11, 12). The literature suggest that this type of intervention can stabilize or to some extent reduce weight when treating children with obesity(12-14).

Previous studies have reported life stressors, societal norms of weight and body size, as well as earlier experiences with the health care system to be the primary determinants for caregivers not letting their children with obesity participate in lifestyle interventions(15-17).

However, no studies have been able to describe if deciding not to participate in a lifestyle intervention potentially affect the psychosocial well-being in children with obesity.

Objective

To investigate the impact in psychosocial well-being for children with obesity deciding not to participate in a family-centered lifestyle intervention (deciding not to participate group) compared to children who attended the intervention (intervention group), and to children never invited into the intervention (non-intervention group). As a secondary objective, we aim to investigate the effect that is not caused by the weight change by adjusting for this.

Material and methods

Design

This is an observational cohort study investigating the impact in psychosocial well-being for children with obesity deciding not to participate in a lifestyle intervention. Data will be obtained from mandatory health check-ups at school, Danish national registries, and Danish National Well-being Questionnaire (DNWQ).

Participants

Children were screened by a community health nurse during school time. If the child's BMI (age- and sex-adjusted) was above 30 kg/m^2 , the parents would be informed and invited to participate in the local lifestyle intervention. If the parents accepted, they would be referred to the intervention. The intervention had a maximum duration of one year and typically consisted of 3-4 consultations with a specialized community health care nurse.

This study will include children with obesity with an inclusion visit between August 1st, 2014, and June 30th, 2020, from the city of Aarhus. February 1st, 2023, will be the last day of follow-up (figure 1). The inclusion visit will be defined as the day of deciding not to participate in the intervention (decided not to participate group), the first day of attending the intervention (intervention group), or the first observation with obesity (non-intervention group).

The groups

- Decided not to participate group: Children with obesity declining to participate in a lifestyle intervention.
- Intervention group: Children with obesity who attended the lifestyle intervention.
- Non-intervention group: Children with obesity never invited into the intervention.

Inclusion criteria

1. An inclusion visit between August 1st, 2014, and June 30th, 2020 (figure 1).
2. Obesity at time of referral as defined by the International Obesity Task Force (IOTF) guideline(18).
3. A measure of weight and height within 6 months before or after time of inclusion
4. Age at inclusion between 5 to 10 years of age.
5. A completed DNWQ at inclusion:
 - The deciding not to participate / non-intervention group - with a timeframe between 6 months prior to and 6 months after inclusion.
 - The intervention group - with a timeframe between 10 months prior to and 2 months after inclusion.
6. A completed DNWQ at follow-up (1 to 3 years after inclusion).

Exclusion criteria

1. Children first decided not to participate, but subsequently accepting the intervention.

Outcome

The outcome of this study will be the dichotomized responses at follow-up to specific items obtained from the DNWQ. The DNWQ is used to examine how primary school children perceive their psychosocial well-being and learning environment in school. The DNWQ has been a mandatory assignment for the public schools in Denmark and was introduced in 2015. DNWQ consist of 20 items for children in 0th to 3rd grade assessed using a three-point Likert scale ranging from 1 to 3. For children in 4th to 9th grade the DNWQ consist of 40 items assessed on a five-point Likert scale ranging from 1 to 5.

For this study we have selected 7 items to best describe the psychosocial well-being in our cohort. We will include completed questionnaires at time of inclusion and at follow-up. At follow-up, we will prioritize completed questionnaires closest to two years from time of inclusion visit.

All answers will be dichotomized into: Good well-being / Poor well-being, depending on the item. Responses 1 and 2 for grades 0-3 and response 1-3 for grades 4-9 will be characterized as poor well-being.

The psychosocial well-being items:

Question 1:

Are you happy with your school? (0th to 9th grade)

Question 2:

Do you feel lonely at school? (0th to 3rd grade)

Do you feel lonely? (4th to 9th grade)

Question 3:

Is anyone teasing you so that you feel sad? (0th to 3rd grade)

Have you been bullied this school year? (4th to 9th grade)

Question 4:

Does your stomach ache when you are at school? (0th to 3rd grade)

How often does your stomach ache? (4th to 9th grade)

Question 5:

Are you good at solving your problems? (0th to 3rd grade)

How often can you find a solution to problems, just by trying hard enough? (4th to 9th grade)

Question 6:

Can you concentrate during class? (0th to 9th grade)

Question 7:

Are you good at helping each other in class? (0th to 3rd grade)

Most students in my class are friendly and helpful. (4th to 9th grade)

Data sources and study variables

Data sources

TM-Sund: TM-Sund is a data capturing tool used by community health nurses and has been used to record data on height and weight obtained from health check-ups at the school and data on children attending or deciding not to participate in the intervention.

The National Registers at Statistic Denmark (DST): DST will be used to identify relevant co-variables such as proxies for Socioeconomic status, immigration background, family structure and psychiatric diagnoses of the child or parents.

The Department of IT and Learning (STIL): The DNWQ will be obtained from STIL, Ministry of Children and Youth.

Study variables:

We wish to include the following co-variates at inclusion:

- BMI z-score (e.g. 3.0 SD) (19)
- Sex (girl/boy)
- Highest completed Household Education (HHE)
 - “Short”: Primary school (UNESCO’s International Standard Classification of Education (ISCED) level 1-2).
 - “Middle”: Highschool, vocational education, and similar shorter education (ISCED level 3-5).
 - “Long”: Tertiary education at bachelor level or higher (ISCED level 6-8)
- Immigration status (Danish origin / immigrants 1. or 2. generation)
- Disposition for mental illness (lifetime) (yes / no)
- Mental illness, child (lifetime) (yes / no)
- Family structure (two caretakers / not-two caretakers)

Statistical methods:

All statistical analyses will be performed using Stata/SE 15 (StataCorp LP, College Station, Texas, USA). All statistical tests will be two-sided with a significance level at 0.05.

For the characteristics at inclusion

- Normally distributed data will be analyzed using a one-way ANOVA (several means) and a t-test (two means).
- Non-normally distributed data will be analyzed using a Wilcoxon ranksum test (2 groups) and Kruskal-Wallis test (> 2 groups).
- Categorical variables will be analyzed using a Fisher's exact test.

For missing data (education, immigration status, and family-type), a multiple imputation (MI) with chained equations will be utilized to replace missing values with imputed values. Rubin's rule will be applied to obtain overall estimates of 100 imputed datasets.

We will perform the analyses in several steps:

Firstly, the McNemar's test will be used to investigate potential change in psychosocial well-being from time of inclusion to follow-up for each of the dichotomized items (Q1-Q7) in all three groups. All items will be dichotomized into: Good well-being/Poor well-being.

Secondly, the impact in psychosocial well-being for children declining participation will be compared to the intervention group and to the non-intervention group by a logistic regression. The logistic regression analysis will be reported as both a crude (only including the outcome and the groups) and a multivariable model. The psychosocial well-being at inclusion will act as an explanatory variable in the models.

The multivariable model will be adjusted for no more than 1 co-variate per 10 observations of the least common outcome. The co-variates are listed in prioritized order: 1) BMI z-score 2) sex, 3) highest completed household education, 4) immigration status, 5) disposition for mental illness, 6) mental illness and 7) family structure.

As an explorative outcome, a logistic regression model adjusted for change in BMI z-score (from inclusion to follow-up) will be performed to remove the potential effect of weight change on the

association between exposure and psychosocial well-being. The BMI z-score observed closest to the included DNWQ at follow-up will be used.

If possible, we wish to investigate the stratified effect of sex, BMI z-score at inclusion, parental level of education, immigration status, disposition for mental illness and change in BMI z score before we examine their potential for effect modification for the impact in psychosocial well-being for the items Q1-Q4 for the decided not to participate group compared to the non-intervention and intervention groups.

Results:

Figure 1:

Lexi diagram for time of inclusion (x-axis), inclusion age of the participants (y-axis), and time points for the DNWQ.

[figure not shown]

Table 1:

Characteristics at inclusion, divided by groups.

	Decided not to participate group	Intervention group	Non-intervention group
	n	n	n
Age at inclusion, median (IQR)			
Sex (% boys)			
BMI z-score at inclusion mean (SD)			
Highest completed household education, n (%)			
Short			
Medium			
Long			
Family type, n (%)			
Two caretakers			
not-two caretakers			
Immigration status (%)			
Danish			
First or second generation immigrants			
Psychiatric diagnosis, child (% yes)			
Parental mental illness (% yes)			

Table 2:

Descriptive presentation of the distribution of answers to each of the items on psychosocial well-being at inclusion and follow-up, divided by groups.

n (%)	Decided not to participate group		Intervention group		Non-intervention group	
	Inclusion	Follow-up	Inclusion	Follow-up	Inclusion	Follow-up
Question 1: Are you happy with your school?						
Good well-being (yes)						
Poor well-being (no)						
Question 2: Do you feel lonely at school? (0-3 grade) Do you feel lonely? (4-9 grade)						
Good well-being (no)						
Poor well-being (yes)						
Question 3: Is anyone teasing you so that you feel sad? (0-3 grade) Have you been bullied this school year? ? (4-9 grade)						
Good well-being (no)						
Poor well-being (yes)						
Question 4: Does your stomach ache when you are at school? (0-3 grade) How often does your stomach ache? (4-9 grade)						
Good well-being (no/rarely)						
Poor well-being (yes/often)						
Question 5: Are you good at solving your problems? (0-3 grade) How often can you find a solution to problems, just by trying hard enough? (4-9 grade)						
Good well-being (yes/often)						
Poor well-being (no/rarely)						
Question 6: Can you concentrate during class?						
Good well-being (yes)						
Poor well-being (no)						
Question 7: Are you good at helping each other in class? (0-3 grade) Most students in my class are friendly and helpful? (4-9 grade)						
Good well-being (yes)						
Poor well-being (no)						

Table 3:

Logistic regression analyses comparing the decided not to participate group and the intervention group.

The multivariable model will be adjusted for up to 1 co-variable per 10 observations.

Decided not to participate group vs. intervention group	OR (95% CI), p-value
Q1 – Enjoyment at school	
Univariable logistic regression	
Multivariable logistic regression	
Q2 – Feelings of loneliness at school	
Univariable logistic regression	
Multivariable logistic regression	
Q3 – Experiences of bullying	
Univariable logistic regression	
Multivariable logistic regression	
Q4 – Experiences of stomach aches	
Univariable logistic regression	
Multivariable logistic regression	
Q5 – Problem-solving	
Univariable logistic regression	
Multivariable logistic regression	
Q6 – Concentration in the classroom	
Univariable logistic regression	
Multivariable logistic regression	
Q7 – Helpfulness in the classroom	
Univariable logistic regression	
Multivariable logistic regression	

Table 4:

Logistic regression analyses comparing the decided not to participate group and the non-intervention group.

The multivariable model will be adjusted for up to 1 co-variable per 10 observations.

Decided not to participate group vs. non-intervention group	
	OR (95% CI), p-value
Q1 – Enjoyment at school	
Univariable logistic regression	
Multivariable logistic regression	
Q2 – Feelings of loneliness at school	
Univariable logistic regression	
Multivariable logistic regression	
Q3 – Experiences of bullying	
Univariable logistic regression	
Multivariable logistic regression	
Q4 – Experiences of stomach aches	
Univariable logistic regression	
Multivariable logistic regression	
Q5 – Problem-solving	
Univariable logistic regression	

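### Time zero is a different event in each group, and the intervention group's earlier baseline window adds about four months between questionnaires in Table 3; no model includes elapsed time, age or grade

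*Combined protocol and SAP*

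**What the plan says.** The Participants section defines inclusion separately for each group: "The inclusion visit will be defined as the day of deciding not to participate in the intervention (decided not to participate group"; then "the first day of attending the intervention (intervention group), or the first observation with obesity (non-intervention group".

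Inclusion criterion 5 sets the window for the baseline DNWQ. For decliners and never-invited children it is "with a timeframe between 6 months prior to and 6 months after inclusion". For the intervention group it is "with a timeframe between 10 months prior to and 2 months after inclusion". Criterion 6 applies to everyone: "A completed DNWQ at follow-up (1 to 3 years after inclusion". Where several follow-up questionnaires exist, the Outcome section says "we will prioritize completed questionnaires closest to two years from time of inclusion visit", so the target is counted from inclusion and not from the baseline questionnaire.

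Under Statistical methods, "The psychosocial well-being at inclusion will act as an explanatory variable in the models". The prioritized covariates are BMI z-score, sex, household education, immigration status, disposition for mental illness, the child's own mental illness and family structure, capped at one per 10 observations of the rarer outcome. The explorative model adds only change in BMI z-score. Age is an entry criterion (5 to 10 years) and a row of Table 1, but it is in no model. No sensitivity analysis on timing is given.

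**The concern.** Two features of the timing differ by group, and neither is adjusted for.

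The first is the starting event. Never-invited children start at their first recorded obesity. Decliners and participants start at a later step of the pathway: screening, invitation, then a decision or attendance. Age and duration of obesity at time zero may therefore differ between groups.

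The second is the age of the baseline answer. The models adjust for that answer but not for how long before follow-up it was given, and the intervention group's window lies earlier.

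Timing matters for this outcome because the instrument changes at 4th grade. The scale goes from three points to five, poor well-being goes from responses 1-2 to responses 1-3, and several items are reworded. Children included at 5 to 10 years and followed for 1 to 3 years can cross that boundary. A group that is older, or observed over a longer interval, can have a different mix of outcome definitions. An odds ratio read as the effect of declining could then partly reflect age, questionnaire version or elapsed time.

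**Working it through.** The plan states no interval between questionnaires, so there is no figure to reproduce. The intervals follow from the windows.

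**Inputs, in months from inclusion**
- Baseline window, decliners and never-invited (criterion 5): -6 to +6, midpoint 0.
- Baseline window, intervention (criterion 5): -10 to +2, midpoint (-10 + 2)/2 = -4.
- Follow-up window, all groups (criterion 6): 12 to 36.
- Follow-up target, all groups (Outcome): 24.

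**Widest allowed interval** (earliest follow-up minus latest baseline, to latest follow-up minus earliest baseline)
- Decliners and never-invited: 12 - 6 = 6 to 36 + 6 = 42 months.
- Intervention: 12 - 2 = 10 to 36 + 10 = 46 months.

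**Interval when follow-up falls on the two-year target** (24 minus baseline time)
- Decliners and never-invited: 24 - 6 = 18 to 24 + 6 = 30, midpoint 24 months.
- Intervention: 24 - 2 = 22 to 24 + 10 = 34, midpoint 28 months.
- Shift: 28 - 24 = 4 months, or 4/24 = 17% longer. It arises wholly on the baseline side.

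**By contrast**
- Table 3 (decliners against intervention): the 4-month shift applies.
- Table 4 (decliners against never-invited): both windows are -6 to +6, so the built-in shift is 0. Individual intervals still vary from 6 to 42 months without adjustment.

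**Two illustrations, on assumptions that are not in the documents**
- Dates spread evenly within each window: mean interval 24.0 against 28.0 months. Baselines taken before inclusion are 6/12 = 50% in decliners and 10/12 = 83% in the intervention group.
- Questionnaires exactly 12 months apart, baseline spread evenly, follow-up the one nearest month 24: every decliner has a 24-month interval. An intervention child with a baseline before -6 has a third-year questionnaire nearer to month 24 than the second-year one, so 4/12 = one third have 36 months. The mean is (2/3) × 24 + (1/3) × 36 = 28 months.

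**Common baseline window**
- The overlap of the two windows is -6 to +2. At the target it gives 24 - 2 = 22 to 24 + 6 = 30 months in both groups. Under the annual schedule above, everyone in it has 24 months.

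**Calendar check**
- From 30 June 2020, the last inclusion day, to 1 February 2023, the last day of follow-up, is about 31 months. The 24-month target is reachable in all groups.

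**The case against.** The earlier intervention window is plausibly deliberate, to keep most baseline answers free of any intervention effect. The plan does not say so, but the aim would be sound. It is a reason to keep the window. It does not remove the unequal interval or explain why elapsed time is left out of the models.

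Follow-up is anchored alike in all groups, and the two-year priority pulls intervals away from the extremes of 6 to 42 and 10 to 46 months. That stands: the built-in gap is 4 months on about two years.

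Screening above the cut-off leads to an invitation, so the lag from observed obesity to decision or attendance may be short. That is possible. But the plan also has children with obesity who were never invited, so an observation of obesity did not always lead to an invitation, and no lag is stated.

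Three stronger readings are tempting and are not supported:
- A reader might infer that all contrasts run over different intervals. Decliners and never-invited children have identical windows, so Table 4 has no built-in difference.
- A reader might take the width of the age range, 10 - 5 = 5 years, as the largest gap between first obesity and decision. The age criterion applies at inclusion, not at first obesity, so it does not bound that gap.
- A reader might conclude that inclusion should be redefined in all groups as the qualifying check-up. TM-Sund "has been used to record data on height and weight obtained from health check-ups at the school and data on children attending or deciding", but the plan does not say that it records which check-up led to an invitation. Moving the date would also leave the baseline window open and could put some baselines after attendance began.

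**Conclusion.** The point holds in a limited form. In Table 3 the windows build in a 4-month longer interval for the intervention group (midpoints 28 against 24 months at the two-year target), and no model corrects for it. The midpoints describe the windows. Equal mean intervals are not excluded, because actual dates within the windows are not given.

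In Table 4 the weakness is the different starting event alone. Its lag, and its effect on age or duration of obesity, cannot be sized from the documents. Both contrasts lack a term for age or grade despite the change of instrument at 4th grade. Neither the size nor the direction of any bias in the odds ratios can be calculated. This is an adjustment and reporting gap that should be closed; it does not show that the comparisons are invalid.

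**What to change.** Keep the stated inclusion dates as the primary definition, and make these changes:

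1. Force two terms into the multivariable logistic models ahead of the prioritized list: months between the baseline and follow-up DNWQ, and age (or grade) at inclusion.
2. Report by group the time from inclusion to each questionnaire and the time between questionnaires.
3. Add a sensitivity analysis of Table 3 restricted to children whose baseline DNWQ falls between 6 months before and 2 months after inclusion, the window common to both groups.
4. Where TM-Sund allows the qualifying check-up to be identified, add a common time zero as a further sensitivity analysis, not as the primary definition.

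The first three changes use dates the plan already needs. The main cost is one or two places under the covariate cap. If the forced terms count, two of them need 2 × 10 = 20 observations of the rarer outcome before any listed covariate enters, so lower-priority covariates may drop out of models with few events. The restricted analysis has a smaller sample. Adjustment for elapsed time may rest partly on extrapolation where the groups' intervals do not overlap (at the target, 18 to 22 months occurs only in decliners and 30 to 34 only in the intervention group). The restricted analysis is the check on that.

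### Baseline BMI may be measured up to 6 months after inclusion, so in the intervention group it can be an on-programme value, and no rule prefers a measurement on or before inclusion

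*Combined protocol and SAP*

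**What the plan says.** - **Window.** Inclusion criteria, item 3, requires "A measure of weight and height within 6 months before or after time of inclusion". It makes no distinction between groups.
- **Time zero.** Under Participants, inclusion is the day of declining (decliners), the first day of attendance (intervention group), or the first time obesity was recorded (non-intervention group).
- **Programme length.** Participants also states: "The intervention had a maximum duration of one year and typically consisted of 3-4 consultations".
- **Questionnaire window.** Item 5 does differ by group. The intervention group's baseline DNWQ is accepted "with a timeframe between 10 months prior to and 2 months after inclusion". For the other two groups the window is "with a timeframe between 6 months prior to and 6 months after inclusion".
- **Use of baseline BMI.** Study variables lists BMI z-score among the covariates at inclusion, and Statistical methods gives it first priority. The exploratory model, which serves the secondary objective, is described as "a logistic regression model adjusted for change in BMI z-score (from inclusion to follow-up) will be performed".
- **Selection rule.** Statistical methods says which follow-up BMI is used (the one nearest the follow-up DNWQ). Nothing says which baseline BMI is used when several fall in the window, or that an earlier one is preferred.

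**The concern.** A baseline covariate should precede the exposure. Here the window runs 6 months past time zero, and in the intervention group that time is spent in the programme. The Introduction itself says that such programmes can stabilise or somewhat reduce weight, so the BMI may already have moved.

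Three uses of the variable are affected:

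- **Multivariable models.** Adjusting for a BMI that attendance has already influenced can remove part of the contrast these models are meant to estimate.
- **BMI change.** Change counted from a late value covers a shorter period and leaves out whatever happened earlier.
- **Descriptive and subgroup work.** Table 1 and the planned stratification by BMI z-score at inclusion and by BMI change use the same values.

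The plan narrows the post-inclusion side of the window for this group's questionnaire but not for its BMI, and gives no reason for treating the two differently.

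**Working it through.** The plan gives no figure to reproduce. The check is timing arithmetic plus a comparison by group.

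**Inputs.** Latest baseline BMI is +6 months (item 3). Latest baseline DNWQ in the intervention group is +2 months (item 5). Programme length D is at most 12 months (Participants). Lengths of 9 and 6 months are my assumptions, because only the maximum is stated.

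**Step 1: share of the programme period elapsed.** Share = m / D, where m is the month of measurement after the start.

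| D (months) | m = 6 (BMI limit) | m = 3 | m = 2 (DNWQ limit) |
|---|---|---|---|
| 12 | 6/12 = 50% | 3/12 = 25% | 2/12 = 17% |
| 9 (assumed) | 6/9 = 67% | 3/9 = 33% | 2/9 = 22% |
| 6 (assumed) | 6/6 = 100% | 3/6 = 50% | 2/6 = 33% |

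Because 12 months is the maximum, 50% is the smallest share that can have elapsed at +6 months.

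**Step 2: what this could mean for BMI change.** Assume the z-score moves linearly during the programme and is flat before it; the documents do not say this. The part of the programme-period change still captured is then 1 − m/D. For D = 12 this is 50% at m = 6, 75% at m = 3 and 83% at m = 2.

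The group average is milder. If measurement dates were spread evenly from −6 to +6 months (also assumed), half the children would have a pre-start value and capture 100%. The other half would average m = 3:

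- D = 12: 0.5 × 1 + 0.5 × (1 − 3/12) = 0.875, about 88%
- D = 9: 0.5 × 1 + 0.5 × (1 − 3/9) = 0.833, about 83%
- D = 6: 0.5 × 1 + 0.5 × (1 − 3/6) = 0.75, or 75%

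**Step 3: meaning of a late value in each group.**

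- *Intervention:* on-programme and post-exposure.
- *Decliners:* off-programme, since those who later accept are excluded. It is still after the decision, which is the exposure under study.
- *Non-intervention:* inclusion is itself an observation of obesity, so a measurement on that day should exist and a late value should rarely be needed.

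**Step 4: the change-adjusted model.** Let b be the true baseline z-score, f the follow-up z-score, and b* = b + e a late baseline, where e is the early change. The recorded change is d* = f − b* = (f − b) − e.

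- With d* alone in the model, e is missing from the adjustment.
- With b* and d* both in the model, b* + d* = f. The model is then equivalent to adjusting for b* and f, so attained BMI is still fully adjusted for and the error sits in the baseline term.

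Statistical methods does not list the other covariates of this model, so the documents do not settle which case applies.

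**The case against.** The strongest reply is that item 3 is an eligibility rule. It requires that a measurement exists and does not say that a late one becomes the covariate; Study variables asks for values at inclusion. The order of events also helps: children are screened, invited, referred and only then attend, and item 2 requires "Obesity at time of referral as defined by the International Obesity Task Force (IOTF) guideline". Most intervention children should therefore have a pre-start value, and the late case may be rare.

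Part of this stands. The frequency is unknown, and the plan may well be carried out sensibly. But item 3 is the only timing rule for baseline BMI, and nothing makes the referral value the covariate. A child whose only in-window measurement falls after the start is eligible as written and would enter with a post-exposure baseline.

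A reader might go further and infer three things that the documents do not support:

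- **That the error sits in one group and touches only Table 3.** A late value in a decliner is post-decision too, so the comparison with the non-intervention group (Table 4) can also be affected.
- **That the weight pathway is under-removed.** This does not follow if baseline BMI and BMI change are both in the model (Step 4).
- **That half of the programme's BMI change is lost.** That is the boundary case, under an assumed linear change over 12 months.

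**Conclusion.** The point holds as a gap in the rule for baseline BMI and should be corrected. The text permits a post-inclusion value in every group and an on-programme value in the intervention group. At the +6 month limit at least 50% of the programme period has elapsed, against 17% of a 12-month programme at the limit already set for that group's questionnaire. These shares need only the stated window and the maximum programme length.

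Any statement about the amount of BMI change missed rests on assumed linearity and assumed measurement dates. The documents give neither the number of children concerned nor an expected BMI change, so no effect on an odds ratio can be derived. The direction of bias in the change-adjusted model is also open. The crude models do not use BMI and are unaffected. The change-adjusted model is labelled exploratory in Statistical methods, although the Objective section makes it the secondary objective.

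**What to change.** Add a selection rule to item 3 and Study variables:

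1. In all groups, BMI z-score at inclusion is the last measurement on or before the inclusion date, within the existing 6-month look-back.
2. A later value is used only if none exists in that look-back. For the intervention group it must fall no later than the +2 months already used for its DNWQ.
3. BMI change is computed from this value.
4. A sensitivity analysis excludes children whose baseline BMI was measured after inclusion.

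It would also help to report, by group, how many children use the fallback, and to list the covariates of the change-adjusted model so that Step 4 is settled.

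**Cost.** A few sentences and a re-selection of TM-Sund records, which hold both the measurements and the attendance data. Some baseline values will be older, which matters somewhat in growing children, although the 6-month look-back limits this. A few children with only a late measurement may be lost. A fallback value at up to +2 months in the intervention group is still on-programme, which is why the sensitivity analysis is needed.
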